### 9.6.2 IgA, IgG and IgM

The total IgA, IgG and IgM levels as well as change from baseline will be summarized descriptively by treatment and visit.

## 9.7 EFFICACY ANALYSES

All efficacy analysis will be performed using the FAS based on subject's randomized treatment. Sensitivity analysis of DAS28 at week 24 will also be performed using the per-protocol analysis set based on the actual treatment the subject received.

Analyses will be performed for two different time periods:

1. From day 1 until week 24 (efficacy analysis visit weeks 8, 12 and 24), only including results prior to 1st infusion of 2nd dose. Subjects who had the 1st infusion of 2nd dose prior to week 24 will have their efficacy endpoints data censored at the timing of 1st infusion of 2nd dose. For example, if disease

Sponsor: Amgen Inc.

Statistical Analysis Plan

Protocol No: 20130108

10-December-2018/ Version 2.0

---

assessment is done at day 1 of week 16 and 1st infusion of 2nd dose is done on the same day, then the disease assessment on day 1 of week 16 will be included in modeling, but any disease assessment after that day will not be included.

2. Day 1 through EOS (efficacy analysis visit weeks 8, 12, 24, 40 and 48). Analyses will be performed separately for all subjects and the subgroup of subjects who received the 1st infusion of the 2nd dose at week 24 (i.e., excluding early retreatment subjects as defined in [section 5.1](#)).

If PK similarity is established between rituximab (US) and rituximab (EU), the 2 arms will be combined into a single reference arm for the primary assessment of clinical equivalence of DAS28-CRP change from baseline at week 24 between ABP 798 and rituximab. The results for ABP 798 vs. rituximab (EU) and ABP 798 vs. rituximab (US) will be provided for descriptive purposes. If PK similarity is not established, the ABP 798 arm will be compared to each of the individual rituximab arms separately to establish clinical equivalence of ABP 798 to the individual reference arms.

The pooling of the reference arms for ACR20/50/70 and hybrid ACR analyses will be conducted similarly.

### 9.7.1 DAS28-CRP

#### PRIMARY STATISTICAL ANALYSIS

##### **DAS28-CRP at Week 24**

The analyses will be performed on the FAS based on the day 1 through week 24 time period described above, with observed data. Subjects with missing baseline DAS28-CRP will not be included in the analysis since no change from baseline can be calculated. Analyses will assess the hypothesis that there are no clinically meaningful differences between ABP 798 and rituximab arms in DAS28-CRP change from baseline at week 24. This primary efficacy endpoint will be tested by comparing the 2-sided 90% CI of the change from baseline at week 24 of DAS28-CRP between ABP 798 and rituximab arms with an equivalence margin of (-0.6, 0.6).

To evaluate treatment differences across time points at which DAS28-CRP was assessed, repeated-measures analysis will be utilized for the day 1 through week 24 time period described above. Data from all assessed postbaseline time points will be included in the analysis. Besides stratification variables, baseline DAS28-CRP value, visit (week), treatment, and treatment-by-visit interaction will be included in the models, with visit as a categorical variable. The adjusted mean with 95% CI for each arm and 90% and 95% CIs for the mean difference will be constructed for mean difference of DAS28-CRP change from baseline between ABP 798 and rituximab arms at each time point.

The mixed model repeated measures analysis will be implemented using PROC MIXED in SAS. Because the time points at which measurements occur are not equally spaced (8, 12, and 24 weeks) and because measurements over time are expected to be correlated, with correlation coefficients being greater for time points that are closer together, a

Sponsor: Amgen Inc.

Statistical Analysis Plan

Protocol No: 20130108

10-December-2018/ Version 2.0

spatial covariance structure denoted SP(POW) in SAS will be used. However, before implementing this structure, its appropriateness will be checked by choosing the smaller Akaike's information criterion when comparing the SP(POW) covariance structure with unstructured covariance structure. Example code for PROC MIXED with three treatment groups is displayed below:

CCI

Note: The contrasts in the lsmeestimate statement may need to be changed depending on the order of the treatments. Only the individual arm comparison SAS code is presented.

### **DAS28-CRP at Other Time Points**

For time period from Day 1 to EOS, the treatment difference and its confidence intervals will be estimated using an ANCOVA model with baseline DAS28-CRP measurement and stratification factors as covariates at each visit window. A sample SAS code for ANCOVA model using PROC MIXED is displayed below:

CCI

Note: The contrasts in the estimate statement may need to be changed depending on the order of the treatments. Only the individual arm comparison SAS code is presented.

### **SENSITIVITY ANALYSES**

To assess the robustness of the DAS28-CRP at week 24 results, the repeated measures analysis described above will be repeated using the PP analysis set based on the day 1 through week 24 time period described above. In addition, DAS28-CRP change from

Sponsor: Amgen Inc.

Statistical Analysis Plan

Protocol No: 20130108

10-December-2018/ Version 2.0

baseline at week 24 will be analyzed using ANCOVA adjusting for stratification factors and baseline DAS28-CRP results.

A sensitivity analysis will also be done to explore the impact of the baseline covariates in [section 9.4](#) on DAS28-CRP at week 24 in addition to the stratification factors. A stepwise model selection (with  $<0.25$  p-value to enter the model and  $<0.1$  to stay in the model) will be fit using PROC GLM and will be used to determine if any of the covariates have significant impact on the outcome variable. The final repeated measures model will be fit using PROC MIXED and will maintain treatment, the stratification factors, baseline DAS28-CRP, visit and visit by treatment regardless and the covariates identified by the stepwise model and the same covariance structure selected in the primary statistical analysis regardless. This additional exploration will be performed on the FAS based on the day 1 through week 24 time period described above.

Additional sensitivity analysis considering the drop-out and missing value will be described in the [section 9.7.4](#).

In addition, for each subgroup (described in [section 4.4](#)) the DAS28-CRP at week 24 will also be examined in the subgroups. These additional explorations will be performed on the FAS based on the day 1 through week 24 time period described above by using the repeated measures analysis with the same covariance structure chosen in the primary statistical analysis. The 90% CI and 95% CIs of difference in mean change from baseline of DAS28-CRP will be displayed.

The DAS28-CRP change from baseline will be plotted by treatment and visit for the FAS with adjusted mean and 95% CI.

### 9.7.2 ACR 20/50/70

The analyses of ACR20/50/70 are descriptive. The RR of ACR20/50/70 at week 8, week 12 and week 24 (refers to the analysis visit) will be analyzed based on the day 1 through week 24 time period using a repeated measures analysis, where data are included as observed for both FAS and PP, unless otherwise specified. Besides stratification variables, visit week (as a categorical variable), treatment, and treatment-by-visit interaction will be included in the generalized estimating equation (GEE) model assuming a log link and an AR (1) correlation structure. Both 90% CI and 95% CI will be provided.

A sample SAS code for PROC GENMOD with the repeated statement is displayed below:

CCI

Sponsor: Amgen Inc.

Statistical Analysis Plan

Protocol No: 20130108

10-December-2018/ Version 2.0

CCI

Note: The contrasts in the estimate statement may need to be changed depending on the order of the treatments. Only the individual arm comparison SAS code is presented.

The risk difference (RD) of ACR20 at week 8, week 12 and week 24 between ABP 798 and rituximab arms and corresponding 90% and 95% CIs will be displayed based on a GEE model similar to the above model with the link function changed to 'link=identity' and without the exponential transformation option under LSMESTIMATE and LSMEANS statement.

From Day 1 to EOS, the RR of ACR20/50/70 between ABP 798 and rituximab arms and their corresponding CIs will be estimated at each visit (weeks 8, 12, 24, 40 and 48) using generalized linear model (specifically, a log-binomial regression model) adjusted for the stratification factors as covariates with observed data. A sample SAS code for PROC GENMOD is displayed below:

CCI

Note: The contrasts in the estimate statement may need to be changed depending on the order of the treatments. Only the individual arm comparison SAS code is presented.

The RD of ACR20 between ABP and rituximab arms and their corresponding CIs will be obtained, based on a similar generalized linear model with link function changed to 'link=identity' and without the exponential transformation option under LSMESTIMATE and LSMEANS statements.

The adjusted percent of subjects achieving ACR20/50/70 will be plotted by treatment and week for the FAS accordingly.

### 9.7.3 Hybrid ACR

The analyses of hybrid ACR are descriptive. The mean difference of hybrid ACR score at week 8, week 12 and week 24 (refers to the analysis visit) will be analyzed using a repeated measures analysis described in [section 9.7.1](#). From Day 1 to EOS, the mean difference and its confidence intervals will be estimated using an ANOVA model with stratification factors as covariates at each visit window. A similar sample SAS code for it is displayed in [section 9.7.1](#).

Sponsor: Amgen Inc.

Statistical Analysis Plan

Protocol No: 20130108

10-December-2018/ Version 2.0

#### 9.7.4 Methods for Handling Dropouts and Missing Data for Efficacy

For ACR, the determination of ACR20/50/70 response will be based on the data available at each visit (refer to [Appendix 2](#) for handling missing ACR individual components), taking into account prorated tenderness and swollenness of joints.

For the primary DAS28-CRP analysis, the primary repeated measures model will be fit to the observed data. The rate of missing DAS28-CRP at week 24 will be tabulated with reasons, such as missing baseline, incomplete week 24 assessment (missing up to 3 of 4 components), outside of the defined week 24 analysis time frame, missing week 24 component assessments (missing all 4 components), and discontinued from the study early prior to week 24 (day 210).

Tipping point analyses will be performed for the efficacy endpoints of DAS28-CRP change from baseline at week 24 based on ANCOVA model using FAS analysis set to explore the sensitivity of results to violations in assumptions about the missing data (i.e., to various missing not-at-random assumptions). Assumptions (tipping point) under which the 90% CI no longer rules out unacceptable differences in efficacy as determined by DAS28-CRP change from baseline at week 24 between ABP 798 and reference (Rituximab (US) and Rituximab (EU)) will be identified.

In this analysis, all the observed data will be included as non-missing, regardless of adherence to treatment or use of prohibited medication. The analysis will be performed using a general three-step approach:

(1) Multiple imputation will be done using PROC MI to generate multiple (e.g., 10) imputed datasets by imputing missing data assuming monotone missing pattern and that subjects with missing data have, on average, worse or better efficacy compared to those who have values. The mean difference between the (unobserved) missing values and observed values (refer to as shift) can vary independently for the different treatment groups. For this analysis, the shifts for Rituximab(EU) and Rituximab(US) are assumed to be the same.

(2) Each of these imputed datasets (which contains identical values of non-missing data but different values imputed for missing data) is analyzed using standard SAS procedure, e.g., PROC GLM, PROC GENMOD, etc.

(3) Results from all imputed datasets are then combined together for overall inference using PROC MIANALYZE.

For DAS28-CRP change from baseline at week 24, seven equally spaced shifts (-0.9 to 0.9 by 0.3) for the DAS28-CRP change from baseline for subjects with missing data will be explored. A sample SAS code for given shifts is given as follows:

CCI

Sponsor: Amgen Inc.

Statistical Analysis Plan

Protocol No: 20130108

10-December-2018/ Version 2.0

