### 3.1 SAMPLE SIZE CONSIDERATIONS

Approximately 300 subjects will be randomized in a 1:1:1 ratio to receive ABP 798, rituximab (US), or rituximab (EU), stratified by geographic region (North America, Eastern Europe, and Western Europe), seropositivity (rheumatoid factor (RF)-positive and/or anti-cyclic citrullinated peptide (CCP)-positive vs. RF-negative and CCP-negative), and number of prior biologic therapies used for RA (1 vs. >1). The sample size will provide > 90% power to demonstrate similarity on the primary PK endpoints based on an assumption of between-subject variability (as measured by coefficient of variation) of 40%, true geometric mean ratio (GMR) of 1 among ABP 798, rituximab (US), or rituximab (EU), a margin of (0.8, 1.25) and 15% dropout by week 24. PK similarity will

Sponsor: Amgen Inc.

Statistical Analysis Plan

Protocol No: 20130108

10-December-2018/ Version 2.0

be tested between ABP 798 versus rituximab (US) and ABP 798 versus rituximab (EU), each with a significance level of 0.05. The similarity between rituximab (US) and rituximab (EU) will be evaluated as well.

With the planned sample size, there is 94% probability that the 90% CI of the difference between the ABP 798 arm and the pooled rituximab (rituximab [EU] and rituximab [US]) arm and 83% probability that the 90% CI of the difference between test (ABP 798) and reference (rituximab [EU] or rituximab [US]) in DAS28-CRP change from baseline at week 24 will fall into the equivalence margin of  $\pm 0.6$  (EULAR response criteria), assuming a standard deviation of 1.4 ([Volkmann et al, 2010](#)) and true mean difference of 0.

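### About 10 imputations leave seed noise of roughly 0.4 to 0.7 of a grid step in the tipping-point CI limits at 15% missing, so a tipping cell inside the grid can move with the seed

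*SAP*

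**What the plan says.** SAP 9.7.4 sets out a tipping-point analysis of DAS28-CRP change from baseline at week 24, "based on ANCOVA model using FAS analysis set". Its stated purpose is to find the missing-data assumptions under which the 90% CI no longer excludes an unacceptable difference. Step 1 uses "PROC MI to generate multiple (e.g., 10) imputed datasets". The number is an example, not a commitment.

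The values explored are "seven equally spaced shifts (-0.9 to 0.9 by 0.3" DAS28-CRP units). Shifts "can vary independently for the different treatment groups", while "the shifts for Rituximab(EU) and Rituximab(US) are assumed to be the same", so the result is a 7 × 7 table of ABP 798 shift against reference shift.

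The readable text of 9.7.4 gives no seed, no Monte Carlo error criterion and no list of imputation predictors. The sample SAS code is redacted and may contain any of these, so they cannot be called absent from the plan.

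**The concern.** A tipping-point table is read by its boundary: the cell at which a CI limit crosses ±0.6. That reading is only as fine as the simulation error in the limit. A shift applies only to subjects with missing data, so one grid step moves the treatment difference by a small amount, and 10 imputations may not resolve it well.

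In the readable text of SAP 9.7.1 and 9.7.4 this is the only missing-not-at-random check on the week-24 DAS28-CRP result. If its boundary moves with the seed, the report may overstate or understate by a cell how far the missing data must depart from the observed data before equivalence is lost.

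**Working it through.** **Inputs**
- SD: SAP 3.1, "assuming a standard deviation of 1.4", with "true mean difference of 0".
- Sample size: SAP 3.1, "Approximately 300 subjects will be randomized in a 1:1:1 ratio", so 100 per arm, and 200 in the pooled reference.
- Margin and CI: SAP 9.7.1, ±0.6 and a two-sided 90% CI.
- Share missing, f: 15%. SAP 3.1 gives this as dropout by week 24. Using it for missing DAS28-CRP is an assumption.
- Variance explained by the imputation model, R²: not given. Assumed 0 to 0.5. SAP 9.7.1 expects measurements over time to be correlated, so 0 is the unfavourable end.

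**The plan's own figures.** Probability = 2Φ(0.6/SE − 1.645) − 1, with SE = 1.4 × √(1/n₁ + 1/n₂).
- 100 vs 200: SE = 0.1715, giving 93.6% (plan: 94%).
- 100 vs 100: SE = 0.1980, giving 83.4% (plan: 83%).

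The inputs are therefore read as the plan uses them.

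**One grid step.** Shifting one arm by 0.3 moves the difference by 0.3 × 0.15 = 0.045.

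**Noise in the point estimate, m = 10, R² = 0.** Between-imputation variance B = 1.4² × (1/n₁ + 1/n₂) × f/(1 − f).
- Pooled: 1.96 × 0.015 × 0.1765 = 0.00519, and √(B/10) = 0.0228.
- Single reference: 1.96 × 0.020 × 0.1765 = 0.00692, and √(B/10) = 0.0263.

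**Noise in the CI limit.** The half-width also varies, because B is estimated from 10 draws.
- Pooled: total variance is about 1.96 × (1/85 + 1/170) + 0.1 × 0.00519 = 0.0351, with root 0.187. The SD of the estimated B is 0.00519 × √(2/9) = 0.00245. The half-width SD is then 1.645 × 1.1 × 0.00245/(2 × 0.187) = 0.012. Combined: √(0.0228² + 0.012²) = 0.026.
- Simulation (Bayesian regression imputation by arm, Rubin's rules, 1,500 seeds on each of 12 data sets) gives 0.0258 pooled and 0.0307 single.

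**Simulated SD of the limit divided by one one-arm step, f = 15%, m = 10**

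| R² | Pooled | Single |
|---|---|---|
| 0 | 0.57 | 0.68 |
| 0.3 | 0.48 | 0.53 |
| 0.5 | 0.39 | 0.45 |

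With less missing the ratio rises: 0.47 to 0.79 at f = 10%, and 0.61 to 1.01 at f = 5%, over the same R² range and both comparisons. If both arms move one step in opposite directions it halves (0.29 and 0.34 at f = 15%, R² = 0).

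**Effect on the reported cell.** Suppose a boundary lies in the grid, equally likely anywhere within a step, and the noise is common to all cells. Two seeds then give different cells with probability 56% at ratio 0.57 and 62% at 0.68. At ratios of 0.4 and 0.5 the figures are 43% and 52%.

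**Is there a boundary in the grid?** At f = 15%, R² = 0 and an observed difference of 0:
- Pooled: the upper limit is 1.645 × 1.4 × √(1/85 + 1/170) = 0.306. The largest contrast, 1.8, adds 1.8 × 0.15 = 0.27, giving 0.576. No cell tips.
- Single: 0.353 + 0.27 = 0.623. The extreme corner tips.

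For the pooled comparison an observed difference beyond ±0.024 (0.6 − 0.576) is enough to tip a corner. With SE 0.186, and given that equivalence holds before shifting (|d| < 0.294), the chance of that is (0.886 − 0.103)/0.886 = 88%. It is about 39% if R² is 0.5 and the ANCOVA removes the same variance. With f = 10% the extreme pooled cell at a difference of 0 is only 0.477.

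**With m = 100, f = 15%.** The ratio falls to 0.18 pooled and 0.20 single at R² = 0, and to 0.12 and 0.14 at R² = 0.5. Two seeds then differ about 20% to 23% of the time at R² = 0.

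**The case against.** Several counter-arguments have force.

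- **Ten is only an example, and the code is redacted.** True. The point is that the readable plan suggests a number too small for the purpose, not that it commits to it. A fixed seed in the code would make the table reproducible, but the cell would still depend on which seed was fixed.
- **A reader might infer a disordered, non-monotone table.** Independent seeds per cell would put about 1 in 9 neighbouring cells in the wrong order: Φ(−0.045/(0.0255 × √2)) = 0.11. Nothing in the SAP calls for independent seeds. With the same draws in every cell, a simulation at these inputs found 0 inversions in 25,200 neighbouring pairs. What remains is an offset common to the whole table.
- **A reader might infer that the noise always exceeds half a step.** At 15% missing that needs an imputation model explaining little. With R² of 0.3 to 0.5 the pooled ratio is 0.39 to 0.48.
- **A boundary may not exist.** This stands as a condition. Less missing data raises the noise ratio but also shortens the grid's reach, so the worst ratios come where a boundary is least likely.
- **A reader might infer that the equivalence conclusion hangs on the seed.** It does not. SAP 9.7.1 bases that decision on the repeated-measures model fitted to observed data. This table is supportive, and efficacy is a secondary objective.

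**Conclusion.** The point holds in conditional form, as a minor improvement. At SD 1.4, 15% missing and 100 per arm, 10 imputations give a seed-to-seed SD of the 90% CI limit of about 0.026 (pooled) to 0.031 (single reference), against a one-arm step of 0.045. When a tipping boundary falls inside the grid, the reported cell can move, typically by about one position. An SD of 0.026 corresponds to 0.026/0.15 = 0.17 DAS28-CRP units of shift.

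The size rests on two quantities the documents do not give: the share of week-24 scores actually missing, and how much variance the imputation model explains.

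**What to change.** In SAP 9.7.4, replace the example of 10 with at least 100 imputed datasets. Use one pre-specified seed and the same draws for every cell of the grid, if the redacted code does not already do so, and say this in the text. Report the Monte Carlo error of the CI limits beside the table, so that a reader can see whether the boundary is resolved to within a cell.

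Going from 10 to 100 cuts the noise about threefold (√10 = 3.2). Seed dependence is reduced, not removed. The cost is computer time only; the estimand, margin and trial conduct are unchanged.

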**CCI**

Note: Only the individual arm comparison SAS code is presented.

### **9.7.5 Multiplicity**

No multiplicity adjustment will be done for efficacy endpoints.

### **9.7.6 Pooling of Sites**

All sites will be pooled together for all analyses.

## **9.8 SAFETY ANALYSES**

All safety analyses will be performed on the Safety analysis set based on subject's actual treatment received. In general, summaries will be provided separately for (1) day 1 to 1st infusion of the 2nd dose of IP (exclusive) for subjects who received 2nd dose or to week 24 (day 175) or EOS (whichever is earlier) for subjects who didn't receive 2nd dose and (2) entire study, unless otherwise specified.

### **9.8.1 Adverse Events**

All reported AEs will be coded to the appropriate SOC and PT according to the most current version of MedDRA, and the severity of each AE will be graded by the investigator per CTCAE v4.03 criteria.

Only TEAE will be tabulated.

Subject incidence of the following AEs will be tabulated by treatment groups and by SOC, PT, and maximum severity grade per CTCAE v4.03:

- treatment-emergent AEs

Subject incidence of the following AEs will be tabulated by treatment groups and by SOC and PT:

Sponsor: Amgen Inc.

Statistical Analysis Plan

Protocol No: 20130108

10-December-2018/ Version 2.0

- treatment-emergent AEs

Subject incidence of the following AEs will be tabulated by preferred term in descending order of frequency in the ABP798 column:

- treatment-emergent AEs
- grade 3 or higher treatment-emergent AEs
- treatment-emergent AEs leading to discontinuation of IP/study
- treatment-emergent AEs leading to infusion delay/infusion not given
- treatment-emergent AEOIs

For treatment-emergent AEOIs, the point estimate and 95% CI for RD of the subject incidence between ABP and the reference product are provided.

Exposure adjusted subject incidence rate (EAIR) of the following AEs will be tabulated by preferred term in descending order of frequency in the ABP798 column for the entire study:

- treatment-emergent AEs
- treatment-emergent AEOIs

The point estimate and 95% CI for RR of the EAIR between ABP and the reference product are also provided.

AEs leading to discontinuation of IP/study are those with an action taken with Investigational Medicinal Product of “dose discontinued” or those with other action taken of “discontinued from study”. If subjects have an AE for action taken with Investigational Medicinal Product of “dose delayed/not administered” checked, that AE leads to the infusion delay/infusion not given. If an AE leads to multiple actions taken with IP, only the last action will be captured in the eCRF.

Counting of AEs will be by subject, and subjects will be counted only once within each SOC or PT. For tables categorized by severity, subjects with multiple events within a particular SOC or preferred term will be counted under the category of their most severe event with that SOC or preferred term.

An overall summary table of treatment-emergent AEOIs will be displayed, providing the number and percent of subjects that are within each AEOI category. In addition, infusion reaction EOIs will also be summarized by PT and maximum CTCAE grade and also by infusion and PT.

A subject listing of AEs leading to discontinuation of IP/ study will be provided.

